9.10. Subsequent Study Visits

At each subsequent visit, the patient's eligibility to the study will be checked and patients will undergo another formal safety assessment before undergoing MR examinations. Patients will have to attend their MRI having fasted for at least 4 hours.

Each follow up visit will ideally take place on a single day but may take place on two separate days, with the first imaging scan and data collection taking place up to 28 days prior to the second imaging scan (see also section 9.7).

Participants will attend follow-up every 180 days for five visits after baseline (total of six visits including baseline). At each subsequent visit, confirmation of continuous consent will be obtained from the participant and an eligibility check will be carried out to ensure that participants still fulfil the inclusion and exclusion criteria.

Study visits will last for 120 minutes and assessments/procedures are as follows:

- Collection of Demographics and Medical History (duration 10 minutes)
- Physical Examination (recording of height and weight) (duration 5 minutes)
- Completion of MRI safety check (5 minutes)
- Clinical care USS (20 Mins)
- nceMRI (20 minutes)
- Completion of EQ-5D-5L and HADS questionnaires at the beginning of each study visit (30 minutes)
- Acceptability of MRI and USS as surveillance test questionnaire (to be completed immediately after the relevant scan on visit 5 only, 30 minutes)

Visit 6, final study visit (120 minutes)

At visit 6, in addition to the other study procedures listed above, a contrast enhanced MRI will be performed on all participants.

Contrast enhanced MRI will also be performed at any visit if the surveillance USS or nceMRI show a suspicious nodule for HCC.

Timing between visits

The baseline visit (visit 1) will be designated as D0. If the study procedures take place on different days for the baseline visit then D0 will be the first day on which study procedures were carried out. Once the baseline visit is completed, dates will be assigned for subsequent visits (visit 2: D180, visit 3: D360; visit 4: D540 etc).

A study visit that takes place within 30 days of the designated visit date will be regarded as a visit that took place on time. Accepting that there will be instances where there are last minute cancellations due to unforeseen circumstances and to allow flexibility in these situations, out of schedule visits will be permitted. Visits taking place between +30 and +90 days of the scheduled visit will be counted as a delayed visit. If the visit cannot be organised within the 90-day window then the visit will be regarded as missed and any procedures taking place more than 90 days after the scheduled visit time, will be assigned as subsequent visit procedures. This schedule will ensure that all study visits are completed within the 30-month window of follow-up.

If only one scanning procedure is performed within the designated visit window, this will be classed as a missed visit.

Examples of study visit timings are set out in Figure 3 below.

Visit 5 – Day 631 (+30)

nceMRI Scan

Visit schedule resets from date of early visit

(D271 +180)

nceMRI Scan

Visit 4 – Day 451 (+30)

Ultrasound Scan

Ultrasound Scan

Visit 6 - Day 811 (+30)

Contrast enhanced MRI Scan

nceMRI Scan

Ultrasound Scan

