7. STUDY DESIGN

This will be a single-arm, multi-centre, prospective cohort study evaluating the diagnostic accuracy of nceMRI and USS for diagnosis of HCC in people at high risk of HCC. People at high risk of HCC include those with liver cirrhosis and a high risk of HCC, or those with previous successfully treated HCC who are back in surveillance with USS. Participants will be recruited from UK hospital-based liver clinics over a period of 18 months and study procedures will take place in UK hospitals and academic centres. Participants will undergo 6 rounds of 6 monthly surveillance with nceMRI and USS over 30 months. Participants will be invited to complete questionnaires at each study visit. Relevant data will also be extracted from the participants' medical records. If at any surveillance round, a surveillance test raises a concern for the presence of HCC, participants will undergo full diagnostic contrast enhanced MRI (ceMRI) to determine whether HCC is present or not. In cases where indeterminate lesions for HCC are reported, these may require further tests including contrast CT, follow-up contrast enhanced MRI, or biopsy as directed by the clinical team. All participants will undergo diagnostic full contrast enhanced MRI at the end of their study participation. If an HCC is diagnosed at any point in the study, then participants will receive treatment according to standard clinical protocols as part of standard of care.

Long-term follow up of medical records from NHS England, the NHS Central Register for Scotland and other patient registries may be conducted for up to 10 years after the end of the active follow up phase. Data obtained from these registries will include but is not limited to liver disease, decompensation episodes, HCC diagnosis, liver transplantation and death. There will be no additional involvement from study sites or participants, as the long-term follow up only involves accessing centrally held medical data.

The overall study design and participant flow is summarised in Figure 1.

Figure 1: AMULET study design and patient flow

Abbreviations: HCC: hepatocellular cancer; USS: ultrasound scan; nceMRI: non-contrast enhanced MRI; AFP: alpha-fetoprotein; HADS: hospital anxiety and depression scale; +ve: positive; -ve: negative [#] see section 9.4 for the description of the procedure for HCC risk estimation

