Participants that complete all 6 rounds of surveillance without a positive surveillance test and without HCC will undergo a contrast enhanced MRI at the end of the study (end of study ceMRI). The diagnostic allocation schedule will be modified for these scans as there will be no opportunity to follow-up LI-RADS 3 and 4 lesions. In these scans LI-RADS 1, 2 and 3 will be classed as not HCC and LI-RADS 4 and 5 lesions will be classed as HCC.

Follow-up for indeterminate lesions beyond 30 months

To enable potential future research, participant consent will be sought to allow follow-up through medical records or through data provided from NHS England, the NHS Central Register for Scotland and other patient registries for up to 10 years after their study participation is completed. This is to allow for collection of data relating to lesions that are still indeterminate at the end of 30 months surveillance period and to evaluate if those without HCC at the end of the study still go on to develop HCC. To facilitate this follow-up, personal identifiable information will be collected and stored centrally with participants' permissions.

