9.13. Early Discontinuation/Withdrawal of Participants

During the course of the study a participant may choose to withdraw early from the study at any time. This may happen for several reasons, including but not limited to:

- The occurrence of what the participant perceives as an intolerable AE.
- Inability to comply with study procedures
- Participant decision

Participants may choose to stop study assessments but may remain on study follow-up.

Participants may also withdraw their consent, meaning that they wish to withdraw from the study completely. In the case of withdrawal before completing the 30 months of study participation and without completing the 6 research visits, the following options for a tiered withdrawal from the study will be available to participants:

 Participants may withdraw from further research visits, and further communication but allow the study team to continue to access their medical records and any relevant hospital data that is recorded as part of routine standard of care; e.g., scans, blood results and disease progression data etc.

- 2) Participants can withdraw from the study but permit data obtained up until the point of withdrawal to be retained for use in the study analysis. No further data would be collected after withdrawal.
- 3) Participants can withdraw completely from the study and withdraw the data collected up until the point of withdrawal. The data already collected would not be used in the final study analysis.

In addition, the Investigator may discontinue a participant from the study MRI procedures at any time if the Investigator considers it necessary for any reason including, but not limited to:

- Pregnancy
- Ineligibility (either arising during the study or retrospectively having been overlooked at screening)
- Significant protocol deviation
- Significant non-compliance with the study requirements Clinical decision (e.g. patient no longer suitable for ongoing surveillance)

Participants who withdraw will not be replaced as the sample calculation already allows for attrition.

The type of withdrawal and reason for withdrawal will be recorded in the CRF.

If the participant is withdrawn due to disease progression or an adverse event, the Investigator will arrange for follow-up visits or telephone calls until the adverse event has resolved or the participants condition optimised.

Procedures to minimise attrition

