Attrition may result due to patients not returning for follow-up visits, or progression of liver disease to Child Pugh stage C or other comorbidities such that surveillance is no longer indicated. To avoid attrition from missed scans, we plan to call participants within two weeks prior to their appointment to remind them of their upcoming visit and participants will be reimbursed for travel and food. To avoid attrition from liver disease decompensation, sites will be asked to manage patients according to National guidelines¹⁰.

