9.14. Definition of End of Study

The end of the study from a participant perspective will be month 30 (visit 6). The end of study will be the date of the final analysis of the data of the last participant.

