Further, we will assess if specific individual-level factors are associated with the diagnostic performance of nceMRI and USS. These will include BMI, gender, age and underlying disease aetiology. For sensitivity, we will assess this by fitting a logistic regression model including all patients with HCC. The dependent variable will be detection via USS/nceMRI, whereas age/BMI and gender will be included as independent variables. Equivalent models will be fitted to determine factors associated with specificity, but this time confined to patients without HCC instead of patients with HCC. A further sensitivity analysis will be conducted in order to compare the sensitivity of nceMRI with USS depending on the USS visualisation scores.

Other considerations relevant to measuring the primary outcome

Alpha-fetoprotein

Alpha-fetoprotein will be measured as part of clinical care at each study visit. In the situation where both USS and nceMRI do not report suspicious lesions (test negative), a contrast enhanced MRI scan will still be needed if:

AFP \geq 20 ng/mL OR doubling of AFP (or more) OR increasing on two consecutive tests.

If an HCC is diagnosed on a ceMRI that was triggered by AFP thresholds rather than by USS / nceMRI, then both USS and nceMRI will be regarded as false negatives

Incidental findings:

Focal hepatic lesions: If an incidental finding is noted in the liver but no further imaging recommended (e.g. simple cysts), scans will be classed as test negative. Lesions in the liver, which are not thought to be HCC, but are considered to require imaging clarification with e.g. contrast-enhanced imaging, will be classed as test positive in the main study endpoint, but will be subject to a planned sensitivity analysis.

Cirrhosis-related complications: If a new ascites is identified on USS or MRI, this will be recorded (small, moderate and large volume). Other non-cancer complications of cirrhosis, such as development of features of portal hypertension, or venous thrombosis will be recorded for both tests.

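### Participants who stop early with negative tests get no reference scan and are removed, so 30-month accuracy rests on a selected group

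*Protocol*

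**What the plan says.** Section 7 (Study Design) states: "All participants will undergo diagnostic full contrast enhanced MRI at the end of their study participation". The operative sections are narrower:

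- Section 9.8.1, on the closing scan: "Participants that complete all 6 rounds of surveillance without a positive surveillance test and without HCC will undergo a contrast enhanced MRI".
- Section 9.10: "At visit 6, in addition to the other study procedures listed above, a contrast enhanced MRI will be performed on all participants". Appendix A marks the scan as routine at visit 6 only.
- Section 9.14 equates the end of the study for a participant with month 30, visit 6.

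Before visit 6 there are two triggers. Section 9.10: "Contrast enhanced MRI will also be performed at any visit if the surveillance USS or nceMRI show a suspicious nodule for HCC". Section 11.2 adds that, with both tests negative, "a contrast enhanced MRI scan will still be needed if" AFP meets any of three criteria.

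Section 9.13 describes several early exits: stopping assessments while staying on follow-up, three tiers of withdrawal, and discontinuation by the investigator. It gives as causes of attrition non-return, or "progression of liver disease to Child Pugh stage C or other comorbidities such that surveillance is no longer indicated". Neither section 9.13 nor section 9.11 schedules a closing scan.

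Section 11.2 bases the 30-month analysis on participants who complete the study. It takes true and false negatives from the end-of-study contrast MRI, and also counts interval cancers and AFP-triggered cancers as false negatives. Section 11.8 requires baseline, visit 6 and at least one contrast MRI, and removes and replaces anyone else. Section 11.4 includes everyone registered. Section 9.13 says withdrawals are not replaced.

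**The concern.** A closing contrast MRI in every participant is what lets the trial find cancers that both surveillance tests missed. If it is done only in those who reach visit 6, verification depends on staying in the study, and the protocol itself links leaving to worsening liver disease and comorbidity. Sensitivity and specificity over 30 months would then describe those who stayed well enough to finish. Double-missed cancers among leavers would be under-counted, which flatters both tests. An analysis plan cannot repair this later, because it cannot supply a scan that was not done.

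**Working it through.** **Who ends up without a reference result.** Taking early leavers by their status at exit:

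| Status at exit | Contrast MRI or diagnosis before exit? | Meets 11.8 read literally? |
|---|---|---|
| Positive ultrasound or non-contrast MRI | Yes (9.10) | No, visit 6 not attended |
| Both negative, AFP criteria met | Yes (11.2) | No, visit 6 not attended |
| HCC diagnosed during the study | Yes (9.8.1) | No, participation ended before visit 6 |
| Both negative, no AFP trigger, no presenting HCC | No | No, neither visit 6 nor contrast MRI |

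Only the last row lacks verification. All four rows fail the visit-6 condition, although section 11.4 would include them all.

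**How many.** Section 9.13 says the sample size allows for attrition, but section 11.3 gives no rate. If 10, 20 or 30% of the 300 stopped before visit 6 (my assumption), 30, 60 or 90 participants would fail the condition. The share in the last row cannot be read from the protocol.

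**Reproducing the plan's figure.** Table 2 requires 50 HCCs for sensitivities of 80% and 50%, by McNemar's test with 90% power and two-sided 5%. The formula is

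n = [1.96·√pd + 1.2816·√(pd − d²)]² / d²,

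where d is the difference and pd the discordant proportion. With a within-person correlation of 0.1 (inferred; the protocol states none):

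- covariance = 0.1 × √(0.8×0.2×0.5×0.5) = 0.02
- pd = 0.8×0.5 + 0.5×0.2 − 2×0.02 = 0.46
- d = 0.3, so n = 49.41, rounded up to 50, as stated.

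The same correlation reproduces all nine sensitivity cells and six of the seven numeric specificity cells. The exception, 98% against 95%, plays no part here.

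**Effect on the sensitivity estimates.** Take 50 HCCs and the same correlation. Assume every HCC found by at least one test is kept, and a fraction f of those missed by both is never verified.

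- Missed by both at 80%/50%: 50 × (0.2×0.5 + 0.02) = 6.0.
- Apparent sensitivity = detected / (50 − f × 6.0).
- f = 10%: 40/49.4 = 81.0% and 25/49.4 = 50.6%.
- f = 30%: 40/48.2 = 83.0% and 25/48.2 = 51.9%.

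At 70%/40%, about 10.1 are missed by both. The same step gives 71.4-74.5% and 40.8-42.6%.

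**Effect on the paired comparison.** In the first case the difference moves from 30.0 points to 15/49.4 = 30.4 and 15/48.2 = 31.1 points. The HCCs that a closing scan would newly reveal in the last row are negative on both tests. They are concordant pairs and add nothing to the discordant pairs that McNemar's test uses. Newly verified controls in that row are likewise true negatives on both tests.

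**The case against.** **Section 7 need not be a promise of an exit scan.** A reader might infer a flat contradiction. Section 9.14 sets the end of the study for a participant at visit 6, and the lay summary places the scan at the end of 30 months, so section 7 can be read as meaning visit 6. That stands. The wording still needs reconciling, because section 9.8.1 also uses the end of participation for an exit at HCC diagnosis, before visit 6.

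**Not every leaver is unverified, and missed cancers are not all lost.** A reader might infer both. The triggered scans, the counting of interval and AFP-triggered cancers as false negatives, continued access to records under the first withdrawal tier, and registry follow-up for up to 10 years all say otherwise. What remains is that later records cannot fix disease status at exit, and that sections 11.2 and 11.8 do not use registry follow-up for the 30-month classification.

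**Power.** A reader might infer that exit scans would restore power lost to attrition. The documents do not support this, because the newly found cancers would be concordant negatives.

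**An exit scan has limits.** On its own it readmits nobody, because section 11.8 also demands visit 6. Those with advanced disease may be the least able to have it. Section 9.8.1 counts LI-RADS 4 as HCC at the end-of-study scan because no follow-up is possible then, which does not carry over automatically to an earlier scan. These points stand and shape the fix.

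**Missing reference results are commonly left to the analysis plan.** This is true of their handling. Here, however, the protocol itself sets the scan schedule and the exclusion rule.

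**Conclusion.** The point holds in a limited form. A participant who stops early with both tests negative, no AFP trigger and no presenting HCC has no reference result and is removed. The visit-6 condition, read literally, also removes verified leavers and contradicts section 11.4. Because leaving is linked to disease progression and comorbidity, the 30-month estimates rest on a selected group.

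The effect on each sensitivity is modest in the illustration: 1 to 3 points for non-contrast MRI and about 1 to 2 for ultrasound at 80%/50%. It depends on the assumed 10-30% of double-missed cancers going unverified, on the inferred correlation of 0.1, and on detected cancers being kept. If section 11.8 were applied literally to HCC cases, that last assumption would fail. The effect on specificity, and the overall effect of a changed case mix, cannot be sized or signed from the protocol. The test of the difference between the two modalities is little affected.

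**What to change.** 1. Reconcile sections 7, 9.8.1, 9.10, 9.13, 9.14 and Appendix A so that the closing contrast MRI already planned is also offered when a participant stops surveillance early without HCC, agrees to it and has no contraindication.
2. In sections 11.2 and 11.8, replace the visit-6 requirement with a valid reference result: a closing contrast MRI at exit, or an earlier reference-standard diagnosis. Align this with section 11.4, and settle whether withdrawals are replaced (9.13 against 11.8).
3. State in advance how LI-RADS 3 and 4 lesions on an early closing scan are classified for the analysis, using record follow-up to the date visit 6 was due where it is available.
4. Report the accuracy results with and without these participants.

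The cost is a protocol amendment and a short change to the analysis text. Nobody has more closing scans than already planned; the scan comes earlier. The drawbacks are that some verified participants will have less than 30 months of surveillance, and that not all leavers will accept or be able to have the scan, so selection is reduced but not removed.

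### Section 9.10 accepts visit 6 as late as day 990, past its own 30-month limit, and gives a later visit 6 nowhere to go, so section 11.8 can drop a participant with a completed closing ceMRI

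*Protocol*

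**What the plan says.** Section 9.10 sets follow-up visits 180 days apart, with a "total of six visits including baseline". A visit within 30 days of its due date is on time. For later visits, "Visits taking place between +30 and +90 days of the scheduled visit will be counted as a delayed visit". One that is still not held by then counts as missed. For its scans the rule reads: "any procedures taking place more than 90 days after the scheduled visit time, will be assigned as subsequent visit procedures". The paragraph closes with a guarantee: "This schedule will ensure that all study visits are completed within the 30-month window of follow-up". None of these rules treats visit 6 differently from the others.

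Visit 6 carries the closing reference standard: at that visit "a contrast enhanced MRI will be performed on all participants". Section 11.2 uses this scan to separate true negatives from false negatives. Section 9.14 ends a participant's study at visit 6, equated with month 30.

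Two sections then define who is analysed. Section 11.8 requires attendance at baseline and at visit 6 plus at least one ceMRI, and removes and replaces anyone who falls short. Section 11.4 includes everyone registered.

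**The concern.** The lateness rule suits visits 2 to 5, where a very late attendance can be counted as the next visit. At visit 6 it breaks down in two ways.

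First, the 90-day allowance carries the last visit past 30 months, so the guarantee is not met.

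Second, a closing attendance more than 90 days late is labelled missed and its scans are sent to a visit that does not exist. Read with the attendance condition in section 11.8, the participant leaves the final analysis even though the ultrasound, the nceMRI and the ceMRI were all done. For someone who never had a positive test, the discarded ceMRI is the scan that establishes whether cancer was present. Section 11.4 would keep the same person, so the protocol gives two answers. If nothing is changed, the choice would be made after the late scans have been read.

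**Working it through.** **Inputs**

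- Visit spacing 180 days, five visits after baseline: section 9.10. Appendix A also shows visit 6 at day 900.
- On-time limit +30 days and delayed limit +90 days: section 9.10.
- Stated limit for all visits, 30 months: section 9.10.
- Month length: the protocol defines none. I use 365.25/12 = 30.4375 days, with a 30-day month as a variant.

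**The guarantee**

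Visit 6 due day = 5 × 180 = 900. Thirty calendar months = 30 × 30.4375 = 913 days.

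| Visit 6 falls on | Status in 9.10 | Calendar months | 30-day months |
|---|---|---|---|
| Day 900 | due date | 900/30.4375 = 29.6 | 30.0 |
| Day 930 (+30) | on time | 930/30.4375 = 30.6 | 31.0 |
| Day 990 (+90) | delayed, accepted | 990/30.4375 = 32.5 | 33.0 |

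The due date itself meets the 30-month limit. The latest accepted day exceeds it by 990 − 913 = 77 days. For the guarantee to hold, visit 6 could be at most 913 − 900 = 13 days late in calendar months, or 0 days late with 30-day months. Even the end of the on-time window passes the limit.

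Appendix A prints ±30 days for visit 6. It prints ±28 or ±30 days for every follow-up visit, so it does not single out visit 6 as exempt from the 90-day rule.

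**Beyond day 990**

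Take a participant on the standard schedule with no positive test, whose closing ultrasound, nceMRI and ceMRI are done on day 991.

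1. Section 9.10: more than 90 days late, so visit 6 is missed.
2. Section 9.10: the scans belong to the subsequent visit. There are six visits and this was the sixth, so no such visit exists.
3. Section 11.8: visit 6 was not attended, so the participant is removed, although the requirement of at least one ceMRI is met.
4. Section 11.4: the participant is registered and therefore analysed.

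Steps 3 and 4 contradict each other. Each participant removed this way is 1/300 = 0.3% of the planned cohort. The number of such participants cannot be computed, because the protocol gives no rate of late attendance.

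**The case against.** **The strongest defence.** The 30-month sentence can be read as saying only that delays do not accumulate from visit to visit, with 30 months as the nominal length of five 180-day intervals. Section 11.8 can be read as asking for reference verification rather than punctuality. It accepts a ceMRI that follows a positive test, and a strict visit 6 condition would also remove every participant diagnosed with cancer earlier, since sections 9.8.1 and 9.11 end their visits at diagnosis. On that reading a late but verified participant stays in. Section 11.4 points the same way. Figure 3 is only partly readable here and may show how a late visit 6 is handled.

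**What stands.** These are plausible intentions, but the text does not state them. The sentence promises completion within 30 months, and section 11.8 names attendance at visit 6 as a condition separate from the ceMRI. Section 11.4 shows that removal is not the only written outcome, so the claim is one of conflict between rules and not of certain exclusion.

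**Stronger readings that a reader might infer, and that the documents do not support**

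- *Visit 6 with one surveillance test plus ceMRI counts as missed.* Section 9.10 says "If only one scanning procedure is performed within the designated visit window, this will be classed as a missed visit". One surveillance test plus ceMRI is two scanning procedures on the plain wording. For visits 2 to 5 the label can be reconciled with section 11.8, which keeps one-test visits: missed for the feasibility count, retained for accuracy.
- *Participants on a reset schedule face a much earlier cut-off.* The readable part of Figure 3 has "Visit 6 - Day 811 (+30" with no 90-day limit beside it. Any cut-off derived from it applies the general rule to a fragment of a missing figure.
- *A two-day visit starting on day 990 extends the limit by a further 28 days.* The second scan would fall outside the visit window, which runs against section 9.10.
- *Recruitment closes too early to replace those removed.* The recruitment dates do not bear on whether a late, verified participant should be kept, and section 9.13 says the sample size already allows for attrition.

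**Conclusion.** The concern holds as a minor inconsistency with a small practical consequence. As written, visit 6 is accepted up to day 990 (month 32.5), 77 days past 30 calendar months, so the guarantee in section 9.10 is not met. A later visit 6 has no place in the schedule. Section 11.8 then removes a participant with a completed closing ceMRI, while section 11.4 retains the same person.

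The day count rests on the printed 180-day schedule without a reset and on a month of 30.4375 days; a 30-day month makes the overrun larger. The removal rests on section 11.8 read literally. The number affected is unknown and probably small. Nothing here shows bias in the paired comparison of nceMRI with ultrasound, and none is claimed.

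**What to change.** 1. In section 9.10, replace the 30-month guarantee with the actual limit: visit 6 is due at day 900 and accepted up to day 990, about 32.5 months.
2. In section 11.8, state that a participant with a closing ceMRI is kept even if the scan was done more than 90 days after the visit 6 due date, and bring section 11.4 into line so that both describe the same set.
3. Add a sensitivity analysis restricted to participants who closed within the visit window.
4. Optionally, add one line saying that the missed-visit label for one-scan visits in section 9.10 does not exclude those visits from the section 11.8 analysis.

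The cost is a few sentences and one extra analysis on dates already recorded. The downside is slightly more variable follow-up length, which the sensitivity analysis addresses. The change should be made before closing scans are available, so that whether to keep late participants is not decided with results known.
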